**5.1.1.4 Treatment Assignment and Treatment Group****Table 5-3: Treatment Group Descriptions**

Treatment groups	Full Description	Data Display Description	Included data
1	Placebo	PBO	Sequence 2, Treatment Period 1, and Sequence 3, both Treatment Periods
2	Rozanolixizumab exposure up to 12 weeks	RLZ 12 weeks	Sequence 1, Treatment Period 1, and Sequence 2, Treatment Period 2
3	Rozanolixizumab extended exposure from 12 to 24 weeks	RLZ 24 weeks	Sequence 1, Treatment Period 2

**Table 5-4: Sequence Descriptions**

Sequences	Full Description	Data Display Description
1	Sequence 1: Rozanolixizumab 12 weeks in Treatment Period 1, rozanolixizumab 12 weeks in Treatment Period 2	Seq1: RLZ 12w +RLZ 12w
2	Sequence 2: Placebo in Treatment Period 1, rozanolixizumab 12 weeks in Treatment Period 2	Seq2: PBO+RLZ 12w
3	Sequence 3: Placebo in Treatment Period 1 and Treatment Period 2	Seq3: PBO+PBO

**Table 5-5: Period descriptions**

Periods	Full Description	Data Display Description
	Pre-Screening	Pre-Screening
0	Screening (Day -42 to Day -15)	Screening
1	Run-In (Day -14 to Day -1)	Run-In
2	Treatment Period 1 (Day 1 to Day 84)	TP1
3	Treatment Period 2 (Day 85 to Day 168)	TP2
4	Run-Out (Day 169 to Day 182)	Run-Out
5	Safety follow-up (Day 183 to Day 218, note that if a participant withdraws prior to this point SFU will not take place between Day 183 and 218)	SFU

**5.1.2 Changes to Protocol-Defined Analyses**

According to the protocol, the Baseline for each variable will be taken as the value measured prior to, but closest to, the treatment on Day 1 (Visit 3, Week 1). However, this rule is specific to

efficacy endpoint assessments only. For safety variables the Baseline will be the most recent value prior to the first dose in the Run-In period. The Baseline definitions for all endpoints are summarized in [Section 5.1.1.3](#).

According to the protocol, the mean 7-day pain and fatigue scores after 10 weeks of treatment will be used for the secondary efficacy endpoint analysis. However, it has been clarified in the SAP that this is based on 12 weeks of treatment (Visits 3-14 in Treatment Period 1, and Visits 15-26 in Treatment Period 2).

Per the protocol, as a secondary analysis strategy, dropouts will be imputed as if they belong to the placebo group, under the conservative assumptions that dropouts are due to a lack of drug efficacy. This analysis will not be produced for the CSR.

### **5.1.3 Protocol Deviations**

Important protocol deviations are a subset of protocol deviations that may significantly impact the completeness, accuracy, and/or reliability of the study data (primary or key secondary outcomes) or that may significantly affect a participant's rights, safety, or well-being.

The criteria for identifying such protocol deviations will be defined within the IPD specifications document.

Important protocol deviations will be categorized as follows:

- Inclusion/exclusion criteria deviations
- Incorrect treatment or dose administered
- Procedural non-compliance
- Treatment non-compliance
- Withdrawal criteria deviation

All protocol deviations will be reviewed as part of the ongoing data cleaning and data evaluation process. All protocol deviations will be discussed at data cleaning meetings for identification of individual IPDs and will be classified by the deviation types in the IPD document. IPDs identified at the data cleaning meetings will be listed by planned treatment sequence for the RS and will include the period of onset, deviation type and description. The period of onset of IPDs is derived per the rules stated in Appendix 4 [Section 8.4](#). All IPDs will be summarized by treatment group and period.

At least one Data Evaluation Meeting (DEM) will be performed prior to unblinding for the Early Readout Analysis. During this meeting, attendees will decide whether any study participants or data should be excluded from any of the analysis sets. A final DEM will be performed prior to database lock to confirm the analysis sets prior to the final analysis. The exclusion of any participants and the rationale will be clearly documented within the relevant TFLs.

#### **5.1.3.1 COVID-19 Related Protocol Deviations**

UCB guidance on deviations and amendments related to SARS-CoV2 pandemic states that the identified COVID-19 related protocol deviations need to be reviewed on an ongoing basis in case they collectively or individually may give reason to consider a protocol amendment (for example study design changes or changes to primary analysis methods etc.).

Additionally, at data cleaning meetings and DEMs, entries on COVID-19 impact pages will be reviewed and assessed whether they are also IPDs. In this case, the COVID impacts will be queried to be reported on the protocol deviation log document.

#### **5.1.4 Handling of Dropouts or Missing Data**

Unless otherwise specified, there will be no imputation of missing data.

For Pain and Fatigue NRS, the 7-day average scores will be calculated based on available data. If there are any missing records in the 7-day periods (inclusive of the assessment visit and the following 6 days), the scores will be calculated as the average amongst the recorded scores, ignoring the missing data. A minimum of 3 completed scores are required to calculate the average; otherwise, the average will be treated as missing. Missing data from visits associated with single assessments will not be imputed.

For details regarding PK data, see [Section 5.5.1](#).

Handling missing or partial missing date and time described in Appendix 2, [Section 8.2](#).

#### **5.1.5 Handling Repeated and Unscheduled Measurements**

All repeated and unscheduled measurements will be presented in the data listings, where applicable. Repeated measurements are defined as more than one measurement at the same time point. Unscheduled and repeated measurements will not be used in the descriptive statistics unless otherwise specified.

Assessments performed at the Early Withdrawal (EW) visit and which are within the protocol defined window of a scheduled visit will be assigned to that scheduled visit, and summarized accordingly. If any such data are already recorded at the given scheduled visit, data from the EW visit will not be re-mapped. Data will be re-mapped on a 'per assessment' basis where assessments are grouped as follows:

- All hematology assessments
- All clinical chemistry assessments
- All urinalysis assessments
- Vital signs assessments; systolic blood pressure, diastolic blood pressure, pulse rate and temperature)
  - Re-mapped vital signs assessments will be mapped to the pre-dose time point only.
- Height and weight
- All IgG assessments (total and subclasses)

The grouping above defines which measurements will be retained together for any re-mapping. An individual parameter would not be re-mapped in isolation of the other parameters performed at the EW visit. For example, a measurement of diastolic blood pressure would only be re-mapped together with the other vital signs assessments performed at the EW visit. If at least one data point is already available at the respective scheduled visit (eg, systolic blood pressure), the data at the EW will not be re-mapped.

Re-mapped EW visit data will be displayed in the by visit summary tables only if the assessment was planned for the particular visit.

Assessments performed at the EW visit which are not within the protocol defined window of a scheduled visit will not be mapped to a scheduled visit and will be listed only.

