### **5.6.6 Clinical Laboratory Evaluations**

All laboratory results values (clinical chemistry and hematology) will be listed by study participant, planned treatment sequence, time point and parameter. Changes from Baseline for numeric variables, the reference ranges and a flag to indicate whether values are below the lower limit of the reference range or above the upper limit of the reference range will be presented.

Separate listings of all clinical chemistry and hematology laboratory results for participants who had at least one treatment-emergent marked abnormality (as defined in the abnormality criteria in [Section 8.1.1](#)) during the study will be presented.

Urinalysis results will be listed for all study participants by treatment sequence, and will include changes from Baseline for numeric variables, and the reference ranges (if applicable).

Any additional laboratory variables which were not collected for screening eligibility and are not included in the outputs described previously will be listed separately for all time points collected. These will include the following:

- Serology
- Serum pregnancy test (for women of childbearing potential, if taken post screening)

- Urine pregnancy tests
- Urine toxicology screen (if taken post screening)
- IGRA assessments
- COVID-19 testing (for participants enrolled under Protocol Amendments 1 and 2 only)

Clinical chemistry and hematology parameters will be summarized by planned treatment sequence and periods and time point for both absolute values and changes from Baseline. Summaries will be based on the SS-r.

Treatment-emergent marked abnormalities with abnormalities defined in Appendix 1 [Section 8.1.1](#) will be summarized by clinical chemistry and hematology groups, planned treatment sequence and visit. Treatment-emergent here refers to measurements obtained on or after the date of the first dose of IMP in Run-In, and on or before the earliest date of the following: the last infusion (including Run-Out if applicable) +56 days, final contact date, or death, and which did not meet the abnormality criteria at Baseline.

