#### **5.6.9.5 Potential Drug-Induced Liver Injury (pDILI)**

The number and percentage of participants who meet one or more of the following pDILI criteria at any visit (including unscheduled visits) will be summarized by treatment period and treatment group, based on the SS-r:

- Participants with at least one post-Baseline liver laboratory assessment
- Incidence of potential hepatotoxicity with symptoms potentially associated with hepatitis or hypersensitivity
- Incidence of potential hepatotoxicity with no symptoms potentially associated with hepatitis or hypersensitivity
- Laboratory criteria for pDILI:
  - (AST or ALT  $\geq 3 \times$  ULN) and TBL  $\geq 1.5 \times$  ULN
  - (AST or ALT  $\geq 3 \times$  ULN) and TBL  $\geq 2 \times$  ULN
  - (AST or ALT  $\geq 3 \times$  ULN) and TBL  $\geq 2 \times$  ULN and ALP  $< 2 \times$  ULN (Hy's Law)

In order to meet the above criteria, a study participant must experience the elevation in bilirubin and ALT or AST (and the absence of the ALP elevation) at the same visit. For example, a study participant who experiences a  $\geq 2 \times$  ULN elevation of bilirubin at one visit and a  $\geq 3 \times$  ULN elevation in ALT (or AST) at a subsequent visit has not fulfilled the Hy's law criteria. If participant meets part of one criterion but at least one parameter is unknown, then he/she should not be considered for meeting the criterion.

Additional analyses for liver function tests (LFTs) will be performed to assess the potential for liver toxicities in accordance with the United States Food and Drug Administration guidelines. Per guidelines, the following criteria will be used to define levels of LFT elevation:

- Aspartate aminotransferase (AST):  $> 3 \times$  ULN,  $> 5 \times$  ULN,  $> 8 \times$  ULN,  $> 10 \times$  ULN,  $> 20 \times$  ULN
- Alanine aminotransferase (ALT):  $> 3 \times$  ULN,  $> 5 \times$  ULN,  $> 8 \times$  ULN,  $> 10 \times$  ULN,  $> 20 \times$  ULN
- AST or ALT:  $> 3 \times$  ULN,  $> 5 \times$  ULN,  $> 8 \times$  ULN,  $> 10 \times$  ULN,  $> 20 \times$  ULN
- Total bilirubin (TBL):  $> 1.5 \times$  ULN,  $> 2 \times$  ULN
- Alkaline phosphatase (ALP):  $> 1.5 \times$  ULN

The number and percentage of study participants who meet one or more of the above LFT elevation criteria at any visit (including unscheduled visits) will be summarized by treatment period and treatment group, based on the SS-r.

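### Non-liver laboratory and vital-sign abnormalities seen only at an unmapped Early Withdrawal visit or an unscheduled visit are listed but not counted in the abnormality incidence tables

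*SAP*

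**What the plan says.** SAP 5.1.5 sets the general rules.

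- Unscheduled and repeat results: "Unscheduled and repeated measurements will not be used in the descriptive statistics unless otherwise specified".
- EW results inside a window: those "within the protocol defined window of a scheduled visit will be assigned to that scheduled visit, and summarized accordingly", unless data of that kind are already recorded there. A further condition applies: "Re-mapped EW visit data will be displayed in the by visit summary tables only if the assessment was planned for the particular visit".
- EW results outside every window: "Assessments performed at the EW visit which are not within the protocol defined window of a scheduled visit will not be mapped" to a visit, and they are listed only.

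SAP 5.6.6 says that treatment-emergent marked abnormalities "will be summarized by clinical chemistry and hematology groups, planned treatment sequence and visit". SAP 5.6.7 summarizes vital-sign abnormalities by sequence, period and time point. Neither section makes an exception to 5.1.5, and neither describes a count over all assessments.

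The definition of treatment-emergent is based on dates. In 5.6.6, "Treatment-emergent here refers to measurements obtained on or after the date of the first dose of IMP in Run-In", ending at the earliest of last infusion plus 56 days, final contact or death, with the criterion not met at Baseline. SAP 8.1.1 and 8.1.2 repeat this window.

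The liver section is different. SAP 5.6.9.5 counts participants who "meet one or more of the following pDILI criteria at any visit (including unscheduled visits"), by treatment period and treatment group on the SS-r, and applies the same any-visit rule to the liver function test elevations.

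SAP 5.6.6 also plans separate listings of all chemistry and hematology results "for participants who had at least one treatment-emergent marked abnormality".

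**The concern.** An off-window EW result or an ad hoc sample can meet the SAP's own definition of a treatment-emergent marked abnormality and still have no cell in the table that reports how often such abnormalities occurred. The SAP solves this for liver tests and gives no reason for treating neutrophils, platelets, creatinine, albumin, IgG or blood pressure differently.

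Albumin and IgG are the most exposed. Protocol 10.2 withholds them from sites and other blinded personnel unless a safety alert leads to clinical review, so the adverse event tables are not a dependable second route. The SAP 8.1.1 criteria for them (albumin below 2 g/dL, IgG below 1.09 g/L) match the values in Protocol 7.1.4 that trigger a temporary hold, so these are results a safety reader will look for. With 20 participants planned per sequence, one participant left out moves a sequence's incidence by 1/20 = 5 percentage points.

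**Working it through.** The plan gives no figure to reproduce. The check is whether an EW result can reach the by-visit table, counted in days from the Schedule of Activities.

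**Inputs**
- Weekly visits with a window of ±2 days (Protocol Tables 1-1 and 1-2).
- Post-Baseline hematology and chemistry at Visits 7, 11, 15, 19, 23 and 27, that is Days 29, 57, 85, 113, 141 and 169, and at EOT/EW.
- EW visit as soon as possible and no later than the next scheduled visit (Protocol 7.2.1).
- Planned dropouts: 25% of 60 = 15 (SAP 1.2).
- Assumption, not in the documents: the EW day is uniform over Days 2 to 168, which is 167 days.

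**Laboratory tests**
1. Days inside some weekly window: 2 (after Day 1) + 23 visits × 5 + 2 (before Day 169) = 119. 119/167 = 71%. The window rule alone would leave 15 × (1 − 119/167) = 4.3 participants unmapped.
2. Days inside the window of a visit with planned laboratory tests: 5 visits × 5 + 2 = 27. 27/167 = 16%. Unmapped or not displayed: 15 × (1 − 27/167) = 12.6.
3. If the scheduled laboratory visit was attended, EW results in the two days after it are not re-mapped, because data already exist. Usable days: 5 × 3 + 2 = 17. 17/167 = 10%. Unmapped or not displayed: 15 × (1 − 17/167) = 13.5.
4. If EW always falls exactly on a weekly visit date from Visit 4 to Visit 27, 6 of 24 dates are laboratory visits, or 25%. Not displayed: 15 × 0.75 = 11.3.

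Most of the loss therefore comes from the condition that the test be planned at that visit, since visits are weekly and laboratory tests are four-weekly. The window itself contributes less.

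**IgG** is also planned at Visits 4 and 16 (Days 8 and 92). Step 2 becomes (27 + 10)/167 = 22% and step 3 becomes (17 + 6)/167 = 14%, leaving 15 × (1 − 37/167) = 11.7 to 15 × (1 − 23/167) = 12.9 participants.

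**Vital signs** are planned at every visit, so only the window matters. Days outside every window: 167 − 119 = 48, and 48/167 = 29%. If EW falls on weekly visit dates, the figure is 0%.

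These are counts of participants whose EW results would not be tabulated. They assume that every dropout attends an EW visit. The documents give no rate of marked abnormality, so the number of abnormalities missed cannot be derived.

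**The case against.** The case for leaving the plan alone has real weight. Protocol 9.4.1 asks for abnormalities to be listed and summarized by visit, and the laboratory and vital-sign endpoint is exploratory and tied to scheduled assessments. SAP section 2 plans no formal hypothesis testing. The dedicated listing in 5.6.6 shows every affected participant on chemistry and hematology, and in a trial of 60 a reader can count from it. All of that stands. It lowers the importance of the point, but a listing does not give an incidence by group, and the proposed change keeps the by-visit rows.

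A reader might also infer more than the documents support:

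- *All unscheduled results are lost.* They are not. The rule in 5.1.5 allows exceptions, and 5.6.9.5 is one. Its ALT and AST rows include the threshold of more than 5 × ULN used for marked abnormality, and its bilirubin and ALP rows use lower thresholds that would catch any marked value.
- *No table counts these abnormalities.* Protocol 8.2.5 and 10.3 have clinically relevant laboratory findings and clinically significant laboratory and vital-sign abnormalities recorded as adverse events, and the TEAE tables have no visit restriction. This backstop fails mainly for the blinded tests.
- *Hold and repeat samples are where severe values surface.* Under Protocol 7.1.4 and 8.2.5 such samples usually follow an abnormal result. If that result came from a scheduled sample, the participant is already counted.
- *The comparison is biased towards no difference.* That would need unequal withdrawal between arms, which the documents do not show.
- *Stopping treatment means losing the data.* Protocol 7.1.3 asks that participants who stop IMP stay in the study where possible, and their scheduled visits still count.

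**Conclusion.** The concern holds in a limited form. For non-liver laboratory tests and vital signs, SAP 5.1.5 combined with 5.6.6 and 5.6.7 leaves a result that is treatment-emergent by the SAP's own definition out of every abnormality incidence table when it is seen only at an unmapped EW visit or an unscheduled visit. The effect is an undercount in those tables and is most relevant for albumin and IgG. Nothing is lost from the listings.

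On a uniform EW day, about 10 to 16% of EW days map to a visit with planned hematology and chemistry, so up to about 13 of 15 planned dropouts would have these EW results untabulated. The number is about 11 if EW visits fall on weekly visit dates, and smaller if some dropouts skip the EW visit. For vital signs, 0 to 29% of EW dates are unmapped, depending on the same question. How many abnormalities this would hide, and whether it would differ between arms, cannot be known from the documents.

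**What to change.** In SAP 5.6.6 and 5.6.7, keep the by-visit and by-time-point rows and add one row per criterion for any treatment-emergent assessment, whether scheduled, repeat, unscheduled or EW. Count each participant once per treatment period and treatment group on the SS-r, as 5.6.9.5 does for liver tests. State in 5.1.5 that this row is an exception to its default, and say which date rule places an off-visit result in a period.

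The cost is a few lines of SAP text and one extra row per table. The data are already planned for collection, so no visit or sample changes.

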### **5.1.6 Center Pooling Strategy**

The data from different centers will be pooled for TFLs.

### **5.1.7 Coding Dictionaries**

Adverse events and medical history will be coded using the latest available version of the Medical Dictionary for Regulatory Activities (MedDRA®) (Version 24.1). Medications will be coded according to the World Health Organization Drug Dictionary (WHO-DD) Global B3 (Version 1 Mar 2021). Medical procedures will not be coded.

## **5.2 Study Population Characteristics**

### **5.2.1 Participant Disposition**

Study participant disposition will be listed by planned treatment sequence for the ASP and will include the following information: study participant status (screen failure, completed or discontinued), date of informed consent, date of randomization, date and time of first and last dose of IMP (including during Run-In and Run-Out Periods), date of premature study termination (if applicable), and primary reason for study termination (if applicable). The listing will also include the date and reason for breaking the randomization code (if applicable) as well as the date of final contact for each study participant.

Study discontinuations will be listed by planned treatment sequence for the RS and will include the reason for discontinuation and the period in which the participant discontinued. The period of discontinuation is derived as follows:

- If a participant receives a dose of IMP in the Run-In Period and withdraws prior to the first dose of IMP in Treatment Period 1, then the period of discontinuation is Run-In.
- If a participant withdraws after starting Treatment Period 1 (defined as receiving a dose of IMP during Treatment Period 1) and prior to receiving a dose of IMP in Treatment Period 2 or attending one or more visits between Visit 16 and 26, the period of discontinuation is Treatment Period 1.
- If a participant withdraws after starting Treatment Period 2 (defined as receiving a dose of IMP during Treatment Period 2 or attending one or more visits between Visit 16 and 26) and prior to receiving a dose of IMP in Run-Out, the period of discontinuation is Treatment Period 2.
- If a participant withdraws after starting Run-Out (defined as receiving a dose of IMP during Run-Out, or attending Visit 27 or Visit 28), and did not attend the end of treatment (EOT) visit, the period of discontinuation is Run-Out.

The study discontinuation listing will also include the total number of days on study medication, calculated in the following way:

Total days on study medication = Date of the last dose of study medication (including Run-Out) – date of the first dose in the Run-In Period +1 day

In addition, there will be separate listings for re-screened study participants, of participants who did not meet eligibility criteria, and of visit dates.

Study participant disposition will be shown in tables. The number of participants who screened, the number of screen failures, and reasons for screen failure will be summarized overall (note: re-screened subjects will only be counted once). Additionally, the number of participants who completed the study, the number of participants who discontinued, and reasons for discontinuation of study will be summarized overall and by (planned) treatment sequence and period. The percentages for discontinuation will be calculated based on the number of participants that started each period.

Study participant disposition will also be summarized by site and investigators using the ASP, showing first participant in, last participant out, the number of participants screened, and the number and percentage of study participants included in each of the RS, SS-r, SS-t, FAS, PKS and PDS, overall and for each planned treatment sequence.

Discontinuation due to AEs and the disposition of analysis sets will also be tabulated.

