Table 1-2: Schedule of Activities (Period 2 through End of Study)

Procedure	12-week Treatment Period: 2												Run-out	Run-out	EOT/ EW	SFU/ EOS
	15	16	17	18	19	20	21	22	23	24	25	26				
Visit number	15	16	17	18	19	20	21	22	23	24	25	26	27	28	-	-
Visit window	±2d	±2d	±2d	±2d	±2d	±2d	±2d	±2d	±2d	±2d	±2d	±2d	±2d	±2d	±7d	±7d
Week	13	14	15	16	17	18	19	20	21	22	23	24	25	26	28	32
Day	85	92	99	106	113	120	127	134	141	148	155	162	169	176	190	218

administration and 1 hour after the end of infusion (±15 min). From Visit 20 through Visit 28, the vital signs will be measured approximately 15 minutes prior to IMP administration. At EOT/EW and SFU/EOS Visits, vital signs will be taken only once during the visit.

^c A brief physical examination can also be performed on the occurrence of an adverse event. Brief and full physical examinations should include evaluation for medical history, for signs and symptoms of latent or active TB, and for risk factors for exposure to TB. An IGRA test can be performed any time, at the investigator's discretion.

^d In addition to the EOT/EW and SFU/EOS Visits, a full neurological examination should be performed for any study participant who experiences severe and/or serious headache and/or suspected aseptic meningitis (see Section 10.13).

^e The 24-hr pain and fatigue assessments to be collected for that day only.

^f Daily 24-hr pain and fatigue assessments to be collected every day for a week.

^g To be performed before IMP dosing.

^h On dosing days, PK, ADA, IgG will be taken pre-dose.

ⁱ 10mL at Visit 15, 27, and SFU/EOS.

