4.4 End of study definition

A study participant is considered to have completed the study if he/she has completed all phases of the study, including the SFU Period. Study participants will have an EOT/EW Visit performed 2 weeks after the Run-out Period or upon discontinuation of the study, followed by an SFU/EOS 5 weeks after the Run-out Period.

The end of study is defined as the date of the last visit of the last study participant in the study.

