7.2.1 Study withdrawal criteria

Study participants **must be withdrawn from the study** if any of the following events occur:

1. Study participant withdraws his/her consent.
2. There is confirmation of a pregnancy during the study, as evidenced by a positive serum pregnancy test.
3. The sponsor or a regulatory agency requests withdrawal of the study participant.
4. Removed
5. Study participant has active suicidal ideation as indicated by a positive response (Yes) to either Question 4 or Question 5 of the “Since Last Visit” version of the C-SSRS. The study participant should be referred immediately to a mental healthcare professional and must be withdrawn from the study.

If a study participant withdraws from the study, the following procedures should be completed:

- The study participant should not receive further doses of IMP.
- The study participant should return for an EW Visit scheduled as soon as possible, but no later than the next scheduled visit.
- SFU or EOS Visit should be scheduled 6 weeks after the study participant has discontinued his/her IMP.

Study participants **may be withdrawn from the study**, at the discretion of the investigator, medical monitor, and study physician, if any of the following events occur:

1. Study participant is noncompliant with the study procedures or medications in the opinion of the investigator.
2. Study participant takes prohibited concomitant medications as defined in this protocol (Section 6.5.2).
3. Study participant develops an illness that would interfere with his/her continued participation.

Investigators should contact the medical monitor, whenever possible, to discuss the withdrawal of a study participant in advance.

For the study participants who are withdrawn from the study, the EOT Visit must be scheduled as soon as possible, but no later than the next regular visit. Study participants will be encouraged to complete the SFU Period.

Participants who are randomized but withdraw prior to dosing at Day 1 may be replaced. Replacement study participants will be assigned the same treatment that was assigned to the withdrawn study participant.

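### The SAP's period-of-discontinuation rule leaves some late leavers with no period and gives others two, so discontinuations by period may not sum to the total

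*SAP*

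**What the plan says.** SAP 5.2.1 (Participant Disposition) derives the period of study discontinuation from four bullets: Run-In, Treatment Period 1, Treatment Period 2 and Run-Out. Two of them matter here.

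- Treatment Period 2 applies to a participant who withdraws after starting that period "and prior to receiving a dose of IMP in Run-Out, the period of discontinuation is Treatment Period 2".
- Run-Out covers those who leave once that period has begun. The SAP's meaning of its start is "defined as receiving a dose of IMP during Run-Out, or attending Visit 27 or Visit 28". The bullet then sets a further condition, on the visit that comes next: "and did not attend the end of treatment (EOT) visit, the period of discontinuation is Run-Out".

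There is no bullet for Safety Follow-up (SFU), although SAP Table 5-5 lists SFU as period 5, from Day 183 to Day 218.

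The derived period goes into the discontinuation listing and the disposition tables, where discontinuations and their reasons are shown by planned sequence and period. On the denominator: "The percentages for discontinuation will be calculated based on the number of participants that started each period". SAP 6.1 names the disposition table under 5.2.1 for registry reporting.

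On the protocol side, 4.4 sets the completion standard: "A study participant is considered to have completed the study if he/she has completed all phases of the study, including the SFU Period". Protocol 7.2.1 says of a withdrawing participant: "The study participant should return for an EW Visit scheduled as soon as possible, but no later than the next scheduled visit". Later in the same section it says that "the EOT Visit must be scheduled as soon as possible, but no later than the next regular visit". The schedule of activities treats the two as one visit: "At EOT/EW and SFU/EOS Visits, vital signs will be taken only once during the visit".

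**The concern.** A period-of-discontinuation variable should place every discontinued participant in exactly one period. Three features of these bullets prevent that.

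1. Completion requires SFU, so someone lost between EOT and SFU/EOS is a discontinuation. A Run-Out dose takes that person out of the Treatment Period 2 bullet, and EOT attendance takes them out of the Run-Out bullet. No SFU bullet exists to receive them.
2. The Treatment Period 2 bullet closes only on a Run-Out dose, but the Run-Out bullet opens on a dose or a visit. A participant who attends Visit 27 or 28 undosed, and then misses EOT, meets both.
3. If EOT in the SAP means the combined EOT/EW visit, a Run-Out-dosed leaver who attends the withdrawal visit gets no period, while one who skips it is assigned Run-Out.

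The second route is foreseeable. Protocol 7.1.3 asks that participants who stop IMP stay in the study for outcome data, and Visit 27 is a BPI-SF assessment in the primary model. At stake are the internal consistency of the by-period disposition table and its agreement with the overall count, in a table meant for public registries.

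**Working it through.** The plan states no figure to reproduce. The check applies the two bullets literally to every feasible late-withdrawal state.

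**Inputs.** The two bullets of SAP 5.2.1, the completer definition of protocol 4.4, and the schedule days. The last Run-Out dose (Visit 28) is on Day 176. EOT/EW is on Day 190 ± 7, that is Day 183 to 197. SFU/EOS is on Day 218.

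**Rule as logic**, for a participant who started Treatment Period 2 (TP2) and did not complete SFU:

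- TP2 is assigned if no Run-Out dose was received.
- Run-Out is assigned if (a Run-Out dose was received or Visit 27/28 was attended) and EOT was not attended.

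Three yes/no facts give 8 combinations. A Run-Out dose implies attendance at Visit 27 or 28, which removes 2 and leaves 6. Reading EOT as the combined EOT/EW visit:

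| State | Visit 27/28 | Run-Out dose | EOT/EW | Assigned |
|---|---|---|---|---|
| 1 | no | no | no | TP2 |
| 2 | no | no | yes | TP2 |
| 3 | yes | no | no | TP2 and Run-Out |
| 4 | yes | no | yes | TP2 |
| 5 | yes | yes | no | Run-Out |
| 6 | yes | yes | yes | none |

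Four of 6 states get one period, 1 gets two and 1 gets none.

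**Other reading: EW is a different visit from EOT.** A Run-Out-dosed leaver who attends only EW is then assigned Run-Out, so fault 3 closes. A participant who attends Visit 27/28 undosed and does not attend the scheduled EOT gets both periods whether or not EW is attended. A Run-Out-dosed participant who leaves after the scheduled EOT still gets none. Faults 1 and 2 therefore hold on either reading.

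**Leavers during SFU (Day 183 onward):**

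- dosed in Run-Out, leaves after EOT: no period;
- dosed in Run-Out, leaves from Day 183 but before EOT: Run-Out;
- attended Visit 27/28 but never dosed in Run-Out, leaves after EOT: TP2.

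None of the three is labelled SFU. The interval from scheduled EOT to SFU/EOS, in which fault 1 arises, is 218 − 190 = 28 days.

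**Effect on the table.** Let D be the number of discontinuations, a the number assigned no period and b the number assigned two. The period counts sum to D − a + b, so they equal D only if a = b. When a = b and both exceed zero, the total looks right although individual assignments are wrong.

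**Size per participant.** With 20 per sequence, 1/20 = 5.0 percentage points. With the planned 25% dropout, 20 × 0.75 = 15 remain, and 1/15 = 6.7 percentage points. The documents give no basis for predicting a or b.

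**The case against.** The strongest reply is that EOT in the SAP may mean the scheduled Week 28 visit. SAP 5.1.5 names the EW visit on its own and gives it separate mapping rules. The protocol synopsis describes EOT as the visit for those who finish Run-Out, and 7.2.1 sends withdrawing participants to an EW visit. On that reading fault 3 disappears. This stands, and fault 3 is therefore conditional. It is not dismissed, because the schedule and protocol 4.4 use one combined visit, 7.2.1 uses both names for the withdrawal visit, and SAP 5.1.1.2 itself writes the combined form.

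A second reply is that little depends on the variable. This also stands. No efficacy model or analysis set uses it, AE periods follow separate rules in SAP Appendix 4, and the disposition listing still shows each participant's termination date, reason, last dose and final contact.

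A third reply is that the overlap is only a drafting slip. Probably so: the Treatment Period 1 bullet closes on a Treatment Period 2 dose or a visit, and the Treatment Period 2 bullet lacks the matching clause. But a programmer following the text would still assign both periods.

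Stronger readings that a reader might infer do not hold:

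- That every SFU leaver lacks a period. Only those dosed in Run-Out who leave after EOT do.
- That everyone who attends Visit 27 undosed is counted twice. With EOT attended, only Treatment Period 2 applies.
- That most late leavers cannot be classified. Four of the six feasible states get exactly one period.
- That the overlap misplaces losses from the rozanolixizumab period. The rule classifies leaving the study, not stopping IMP, and someone who attends Visit 27 was still in the study at the last Treatment Period 2 assessment.

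**Conclusion.** Wrong as written, and minor. On any reading of EOT, the rule gives no period to a Run-Out-dosed participant lost between EOT and SFU/EOS, and two periods to a participant who attends Visit 27 or 28 undosed and misses EOT. If EOT is the combined EOT/EW visit, Run-Out-dosed leavers who attend the withdrawal visit also get no period.

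The effect is confined to the discontinuation listing and the by-sequence, by-period disposition table. The period counts may fail to sum to the overall count when such participants occur, by an amount that cannot be predicted from the documents. Overall discontinuation counts, efficacy analyses and AE period assignment do not change.

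This rests on a literal reading of the bullets, on protocol 4.4 defining who is a completer, and on participants who had started Treatment Period 2.

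**What to change.** Replace the last two bullets of SAP 5.2.1 with an ordered, exclusive rule, and delete the condition on EOT attendance:

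- Treatment Period 2: withdraws from the study after starting Treatment Period 2 and before starting Run-Out (a Run-Out dose, or attendance at Visit 27 or 28), whether or not an EOT/EW visit is later attended.
- Run-Out: withdraws after starting Run-Out, with study termination before Day 183, whether or not an EOT/EW visit is attended.
- SFU: started Run-Out and terminates on or after Day 183 without completing SFU/EOS.

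Day 183 is the Table 5-5 boundary. State that it is counted from the first Treatment Period 1 dose, since SAP 5.1.1.1 counts from the last dose once dosing has ended. Add an SFU row to the disposition table, with those who started Run-Out and were still in the study on Day 183 as its denominator.

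Under this rule states 1 and 2 above become Treatment Period 2. States 3 to 6 become Run-Out or SFU according to termination date, so all six get exactly one period, and the meaning of EOT no longer matters. The cost is SAP wording and one derived variable, using dates already collected.
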